
### **1.5 Dose Rationale and Risk/Benefits**

The study will follow a 2x2 factorial design. Two supplements will be used: one will consist of 2 grams of a 3:2 ratio of EPA/DHA consumed orally (4 softgels=4g fish oil) once daily for 6 weeks and another will be 2000 IU daily of Vitamin D (1 capsule). The n-3 PUFA dose has been previously used for studies of other painful conditions and has been associated with a significant increase in the n-3 PUFA level and a reduction in the n-6:n-3 PUFA ratio over a 6 week period. The Vitamin D dose of 2000 IU per day has been previously used in other clinical trials, has been shown to correct Vitamin D to optimal levels, and has been shown to be safe. Participants in the comparator arm for n-3 PUFA will receive 4 grams of soybean/corn oil, which has been safely and effectively used as a comparator in a number of studies.

Chronic pain is associated with reduced mental and physical health and interferes with essential activities of daily life. Currently there are limited treatment options to address chronic pain once it has become established and the overarching aim of this clinical trial is to prevent chronic pain development, therefore there is a critical unmet need of safe, non-addictive, non-invasive preventative treatment options that can

be administered to burn survivors in the aftermath of injury. This study has the potential to benefit participants and future burn survivors and improve pain and general health outcomes. The risks of taking n-3 PUFAs and/or Vitamin D are small. Although n-3 PUFA preparations are well tolerated, potential side effects include fish like taste, belching, indigestion and GI upset, increased bleeding. Acceptance of this limited risk is reasonable based on the anticipated benefits to burn survivors at risk for chronic pain development. Side effects from Vitamin D are rare, however, it is possible that over supplementation of Vitamin D may be associated with headache, loss of appetite, dry mouth, metallic taste, and nausea/vomiting. **The risks to the subjects in experiencing these side effects is balanced against the potential for a new, safe, non-opioid preventative treatment option for chronic pain following MThBI.**

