### **3.3 Primary Study Endpoints**

The primary endpoint of this study will examine the safety, feasibility and efficacy of n-3 PUFAs/Vitamin D to improve chronic pain outcomes following major thermal burn injury. **Outcome to assess safety:** Safety outcomes will be met after descriptive review of adverse outcomes, and comparison of adverse events is made across treatment groups by investigative team at the conclusion of the study. **Outcome to assess feasibility:** 60 patients will be enrolled, randomized into one of 4 treatment arms in a 1:1:1:1 ratio, and treated with study drug for 6 weeks following Major Thermal Burn injury severe enough to warrant surgery within a 24 month period. Proportion of participants completing following up at 6 weeks will be reported. The concentration of Vitamin D and n-3 PUFAs will be calculated before and after the 6 week treatment in each treatment arm to assess the response (expect an increase in both Vitamin D and n-3 PUFA in treatment arms). **Outcome to assess efficacy:** Efficacy of Vitamin D/PUFA will be measured by difference in pain severity in treatment arms versus control arms. We will 1) calculate a model estimated mean of chronic pain severity and corresponding 95% Confidence interval in each study group and 2) determine the slope of pain recovery among individuals treated with Vitamin D and n-3 PUFAs relative to control participants using a linear mixed model adjusting for sex, ethnicity, and study site.

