## **5.4 Text messaged or e-mailed outpatient Weekly Pain and Compliance Assessments**

Brief, weekly assessments of number of missed doses in the past week and graft site pain severity (0-10 NRS) over the past 24 hours will occur via automated text message/e-mailed surveys administered through our secure study database RedCap. If patients are not able to respond via text messaging or e-mail they will be called by investigative team. Patients will be called by study staff if they miss 3 or more doses in a 1 week period to provide counseling and determine any potential barriers to taking the study medication. Study staff will contact the participants at 3 weeks for a brief assessment of missed doses, to provide adherence counseling, and collect any reported information about adverse events. At this time a condensed bleeding assessment will be performed to assess bleeding events since the beginning of treatment.

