## **5.5 6 week assessment**

The goal of this assessment is to perform a comprehensive phenotypic follow-up and perform a blood draw to assess for lipid concentration, Vitamin D concentration and related gene expression (RNA), and epigenetic changes (DNA).

Outcome assessments will be performed via structured and scripted interview/survey either at the burn clinic or via telephone or via a web based survey emailed to their on file email address. Multiple methods of contacting participants may be used to best meet the needs of the participants. Average pain and itch (0-10 NRS), frequency of pain and itch during the past 24 hours at the patient's donor site, as well as average pain and itch (0-10 NRS) and frequency of pain and itch during the past 24 hours at the patient's graft site will be assessed. The condensed bleeding assessment tool will be repeated to assess for bleeding events between the 3 and 6 week timepoints. The presence of neuropathic pain symptoms (DN4, S-LANSS) will also be assessed, as well as pain and itch related interference in daily activities (Brief Pain/Itch Inventory Interference Subscales). Information regarding current medication use (both standing and PRN) and health services utilization (including burn care such as PT, OT) will also be obtained. At these time points the following assessments will also be administered: The frequency of scratching and its effect on itch related to the burn, at either the donor site or the graft site, will be evaluated. The location (Regional Pain Scale) and intensity (0-10 NRS) of pain and itch symptoms (using a modified RPS) in any locations other than the donor and graft sites will be assessed, along with the presence and severity of other somatic symptoms (e.g. headache, dizziness, and itching). General health (SF-12), depressive and anxiety symptoms (DASS), and PTSD symptoms (PSS-I) will be assessed. Sleep quality will be assessed using the MOS Sleep Scale. Global recovery after burn injury will be evaluated using a 0-100 percent improvement scale (0% = no recovery, 100% = completely recovered). Alcohol abuse is common among injured patients, and increased alcohol or drug use after trauma is likely to be related to chronic pain and itch outcomes. Quantity and frequency of alcohol and drug use will be assessed at the 24 week and 48 week follow-up time points, using questions from the TWEAK and Substance Abuse Outcomes Module.

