
## **6 Statistical Plan**

### **6.1 Sample Size Determination**

The purpose of this study is to assess study feasibility, safety and to obtain initial effect size estimates and confidence intervals to use in sample size calculations for a larger study. Previous studies of Vitamin D and n-3 PUFAs for the treatment of chronic pain are poorly generalizable to this setting because 1) they examine treatment of established chronic pain states versus developing pain states, 2) do not involve trauma exposure/acute stress, and 3) are not preventive studies. Therefore, this pilot study will be instrumental in demonstrating feasibility and safety of the protocol, and estimates of efficacy along with confidence intervals will be helpful for planning a larger follow-up study.

**Justification for the sample size.** We will target 15 individuals in each group (60 total) so that feasibility and safety may be determined as well as provide potential evidence for efficacy. Below, calculations are provided to justify sample size for each objective.

**Feasibility:** Assuming that observed follow-up will be around 80%, this study will allow us to estimate follow-up rates to within  $\pm 10\%$  with a 95% confidence interval given we reach the enrollment target of 60. Allowing for up to 20% loss, with 30 participants treated in each n-3 PUFA arm of our study, our study is powered at 90% to detect a difference of 2.6% of DHA (an n-3 PUFA) in total fatty acid content considering a standard deviation of 1.3%. This study (30 per Vitamin D arm) is powered at 83% to detect a change of 9 ng/dl in Vitamin D level assuming a SD of 10.5.

**Efficacy:** Allowing for up to 20% loss and assuming a common standard deviation of 2.6 (approximated from our pilot dataset) and no interaction between treatments, randomizing 30 participants to each comparison group (Vitamin D/n-3 PUFA versus control) will allow us to estimate the difference in mean pain severity to within  $\pm 1.4$  using a two-sided 95% confidence interval.

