## 6.2 Statistical Methods

### Primary outcome assessments and analysis:

**Feasibility:** The primary objective of this pilot study is to ensure that we are able to enroll participants and make follow-up assessments. The subsequent study will be considered feasible if we are able to collect follow-up assessments on >80% of enrolled participants at 6 weeks following MThBI, and >80% of participants at 1 year. Medication adherence will be assessed by pill counts at the end of the study and quantitative determination of plasma fatty acid/Vitamin D concentration. The subsequent study will be considered feasible if at least 75% of participants take at least 80% of their assigned medication (per pill count) and there is a statistically significant increase in Vitamin D and fatty acid concentration in treated individuals versus controls. T-tests will be used and a  $p < 0.05$  will be considered statistically significant.

**Safety:** Another main objective of this pilot study is to ensure safety of both treatments as well as combined. To determine safety, we will tabulate the number of serious adverse events in each treatment arm and perform a descriptive review of adverse events in the study, and make a determination about the degree of relatedness of each adverse event with the intervention using CTCAE criteria outlined in Appendix 2. The recorded adverse events in each arm will be tabulated descriptively, but no inferential statistics (p-values and confidence intervals) for comparing arms will be reported.

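### Section 6.2 Safety counts serious events by arm, asks for no count of participants affected, and does not say how the week 3 and week 6 bleeding assessment will be reported

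*Combined protocol and SAP*

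**What the plan says.** Section 6.2, Safety, states that "we will tabulate the number of serious adverse events in each treatment arm and perform a descriptive review of adverse events in the study". It goes on: "The recorded adverse events in each arm will be tabulated descriptively, but no inferential statistics (p-values and confidence intervals) for comparing arms will be reported". Section 3.3 describes the safety outcome as met once "comparison of adverse events is made across treatment groups by investigative team at the conclusion of the study". For SAEs the unit is the event and the grouping is the arm. For other AEs the grouping is the arm and the unit is not fixed.

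The bleeding data are set out elsewhere. Section 1.5 says of n-3 PUFA that "potential side effects include fish like taste, belching, indigestion and GI upset, increased bleeding". At the week 3 contact (Section 5.4) "a condensed bleeding assessment will be performed to assess bleeding events since the beginning of treatment". At week 6 (Section 5.5): "The condensed bleeding assessment tool will be repeated to assess for bleeding events between the 3 and 6 week timepoints". The two administrations together cover the treatment period. Section 6 gives the instrument no endpoint, summary or comparison.

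On design, Section 3.3 says "60 patients will be enrolled, randomized into one of 4 treatment arms in a 1:1:1:1 ratio". The interim analysis text in Section 6.2 records that the trial ended after the 24th patient.

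**The concern.** The safety question for each supplement is how many exposed people were affected, compared with how many unexposed people. A count of events answers a different question: one participant with repeated events can dominate a small arm, and the number of people affected cannot be worked back from the total.

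Bleeding is the effect the protocol guards against most visibly. Section 1.5 names it, Section 3.7 excludes people with bleeding disorders or on certain antithrombotic drugs, and all participants have surgery planned (Section 3.6). The protocol collects a solicited, bleeding-specific measure but does not say how it will be reported. At stake is whether the report on a primary objective gives the proportion with any bleeding by fish oil exposure, or whether that depends on how each bleed was coded as an adverse event.

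**Working it through.** **1. The plan's own figure.** The documents state no figure for safety or bleeding. The nearest one that uses a supplement margin is the 83% power for vitamin D level in Section 6.1: 30 per group, up to 20% loss, difference 9, SD 10.5.
- n = 30 × 0.8 = 24 per group, df = 46, two-sided alpha 0.05.
- Noncentrality = (9/10.5) × √(24/2) = 2.97, giving 82.8% power by the t-test.

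The figure reproduces, so the plan does use the margin in its sample size reasoning.

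**2. Group sizes.** At 24 enrolled: 24/4 = 6 per arm on average and 2 × 6 = 12 per margin. At the planned 60: 15 and 30. The 6 and 12 assume equal allocation.

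**3. Upper limit on risk when no one is affected** (one-sided 95%), 1 − 0.05^(1/n):

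| n | Limit |
|---|---|
| 6 | 39.3% |
| 12 | 22.1% |
| 15 | 18.1% |
| 30 | 9.5% |

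**4. What the four-arm layout already shows.** For an event with an assumed 10% risk, the chance of at least one case is 1 − 0.9^6 = 46.9% in one arm and 1 − 0.9^12 = 71.8% in 12 people. Across two fish oil arms of 6 it is 1 − 0.9^6 × 0.9^6 = 71.8%, the same figure. Column layout does not change the chance of seeing a case. Zero in both fish oil arms is zero in 12.

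**5. What cannot be recovered.** As an illustration, three events in an arm of 6 could be one, two or three people: 1/6 = 17%, 2/6 = 33% or 3/6 = 50%. Adding columns gives more events, not the number of people.

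**6. Route of a bleed into the tables.**
- Sections 7.1 and 7.2: the AE definition is broad and all AEs must be recorded in the case report form. The adverse event table in Appendix 1 lists bruising and hematoma. By this route a bleed is tabulated.
- Section 7.6: the electronic AE form is required for unanticipated AEs, and an expected AE is a known potential effect of the drug or disease. Section 1.5 names bleeding as such an effect. By this route a bleed could go without a form.

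A bleed reported on the tool can therefore be handled either way.

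**7. Why the table should stay descriptive.** The documents give no bleeding rates. If they were 10% v 30%, two-sided Fisher power is 9.5% at 12 v 12; at 5% v 40% it is 36%. At 6 v 6 the figures are 0.6% and 3%. Neither layout supports a test.

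**The case against.** The case against has four parts.

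- **Nothing is lost by showing four arms.** Both fish oil arms appear, and a reader can add two columns. This stands. A reader might infer from 47% v 72%, or 39% v 22%, that the plan throws away half of those exposed. Step 4 shows that it does not. Only the number of people affected is beyond recovery.
- **Bleeds are adverse events and will be tabulated.** This partly stands. Section 7.2 supports it, and Section 5.4 places the tool in the same contact that collects AEs. It would be too strong to say that the bleeding data go unanalysed. Section 7.6 nevertheless leaves capture uncertain, and the instrument itself has no stated summary.
- **By-arm reporting without inference is deliberate.** This stands. Section 6.2 aims at the safety of each treatment and of the combination, which needs its own column, and omitting p-values and intervals is a reasonable choice for a pilot. A reader might also infer that only safety departs from the factorial structure. In fact Section 3.3 reports pain by study group and concentrations by arm.
- **Event dominance is limited.** Section 7.2 groups related signs under one diagnosis, and the unit for non-serious AEs is left open. This reduces the problem but does not supply a participant count.

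**Conclusion.** The point holds as a gap in specification. Section 6.2 asks for SAE counts and by-arm AE tables, with no participant-level count and no stated use of the solicited bleeding assessment. The documents do not show that participants are discarded, that bleeds are certain to be missed, or that a formal comparison was owed.

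The gain is modest and concrete. It supplies the number of people affected, which event totals cannot give, and a direct pooled statement for fish oil: if no one is affected, a limit of 22% from 12 exposed instead of 39% from a single arm of 6 (9.5% and 18% at the planned size).

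This rests on roughly equal arms at 24 enrolled. Reading the pooled figure as the effect of fish oil also assumes that vitamin D does not alter bleeding. Section 6.1 assumes no interaction for pain and says nothing on this for bleeding.

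**What to change.** In Section 6.2, Safety, specify the number and percentage of participants with:
- at least one SAE;
- at least one AE, by type;
- any bleeding on the week 3 or week 6 tool, with the number assessed as denominator.

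Show each by the four arms and also by n-3 PUFA yes/no and vitamin D yes/no, with event counts in an adjoining column. Keep the tables descriptive, without p-values or intervals between groups, as Section 6.2 intends. State whether bleeds reported on the tool are also entered as AEs, so that Sections 7.2 and 7.6 agree.

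Because enrolment has already stopped, label the bleeding-tool summary as an added descriptive safety table and not as a newly designated safety outcome.

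The cost is a few tables from data the protocol already collects. The downside is that each margin pools over the other supplement, so the four-arm table must stay beside it.

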**Efficacy:** Estimates of efficacy will be obtained via repeated measures analysis using mixed effects models (PROC MIXED in SAS 9.4). Prior to unblinding the data, our study statistician will perform a blind review of the data in which statistical models will be developed and tested using dummy (computer generated) treatment assignments. The goal of this is to fit the most appropriate model given aggregate data. Graft site pain severity will be collected in four waves across time; therefore, we will use mixed effects modeling with random error using an unstructured covariance matrix. The model will include fixed effects for PUFA, Vitamin D, their interaction, time, and the interactions between groups and time, as well as fixed effects for site, gender, and race/ethnicity. During blind review, competing nested fixed effect models will be compared. We will consider modeling time using either a) time as continuous variable with a linear model (i.e., slopes only), b) time as a continuous variable with a higher order polynomial model (up to cubic, given 4 time points), or c) time as a class variable. Competing fixed effect models will be fitted using maximum likelihood and compared using the BIC criterion. Once the form for the fixed effect model is selected, the final model will be fit using restricted maximum likelihood. After unblinding the data, we will use appropriately specified linear contrasts of the model parameters to estimate mean differences across groups at each time point along with 95% confidence intervals.

**Interim analysis:** Two interim analyses are planned after the enrollment of the 20th and 40th patients in the study. This will be conducted to ensure safety, perform a feasibility assessment, and assess potential efficacy. This optimizes study ethics, as it ensures safety of current and future study participants, allows

optimization of study protocol based on results of safety and feasibility assessment, and allows an efficacy assessment with appropriate statistical “penalty” for an interim look. Adverse events will be qualitatively reviewed at two interim analyses occurring after enrollment of the 20th patient and after enrollment of the 40th patient. While study investigators, staff, and participants remain blinded, the study statistician will prepare a qualitative summary of adverse events by type over the treatment groups. The results will be reported to investigators in aggregate such that blinding is maintained.

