Significance thresholds for interim analyses for potential efficacy will be adjusted using the O’Brien-Fleming approach. In order for the trial to stop enrolling because efficacy (superiority) is established after the first interim analysis (after 20 patients enrolled), the boundary critical value of 3.428 and corresponding alpha of 0.0006 must be reached. In order for the trial to stop enrolling because efficacy is established after the second interim analysis (after 40 patients enrolled), the boundary critical value of 2.431 and corresponding alpha of 0.0151 must be crossed. After the final analysis (third analysis) a critical value of 1.985 and a p-value of 0.0471 will be used. This final, adjusted p-value threshold of 0.0471, allows for a statistical “penalty” to be assessed because of the interim look. Given that this is a pilot study, we believe it is critically important to assess our safety, feasibility and potential efficacy outcomes at interim analysis.

Given that the study was terminated early after enrollment of the 24th patient after one interim analysis, the final, adjusted p-value threshold of 0.0492, allows for a statistical “penalty” to be assessed because of the interim look.

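### No small-sample correction is set for the unstructured mixed model, now fitted to 24 patients, so the 0.0492 threshold and the 95% intervals are not assured

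*Combined protocol and SAP*

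**What the plan says.** The Efficacy paragraph of section 6.2 specifies PROC MIXED in SAS 9.4, with "mixed effects modeling with random error using an unstructured covariance matrix". Fixed effects are PUFA, Vitamin D, their interaction, time, groups by time, site, gender and race/ethnicity. Whether time enters as linear, polynomial or class is chosen by BIC during blind review, and the final model is fitted by REML. After unblinding, linear contrasts give mean differences with 95% confidence intervals.

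The interim paragraphs of the same section set O'Brien-Fleming efficacy thresholds:

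- 20 patients: "the boundary critical value of 3.428 and corresponding alpha of 0.0006 must be reached".
- 40 patients: "the boundary critical value of 2.431 and corresponding alpha of 0.0151 must be crossed".
- Final analysis at 60: "a critical value of 1.985 and a p-value of 0.0471 will be used".

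The section then records that "the study was terminated early after enrollment of the 24"th patient, after one interim analysis, and sets "the final, adjusted p-value threshold of 0.0492". No critical value goes with that figure.

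Nowhere do the documents name a degrees-of-freedom method, a t or F reference, or a correction for the estimated covariance. They also do not say which contrast is tested.

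**The concern.** A critical value and an alpha can be paired only once the reference distribution is fixed. The printed pairs are normal ones, whereas contrasts from a REML mixed model are t-type statistics on limited degrees of freedom. Their standard errors also tend to be too small when ten covariance parameters are estimated from a couple of dozen patients and then treated as known. At the planned 60 patients this would matter little. At 24 it can matter.

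What is at stake is less a claim of efficacy than the estimates carried forward. Section 6.1 says the effect estimates and their intervals are meant for planning a larger trial. Intervals that are too narrow would overstate how much this pilot has learned. Section 6.2 reuses similar models for the Brief Pain Inventory and SF-12 scores and adds sex-by-treatment terms to the main model, so the same gap carries over.

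**Working it through.** **Inputs from the documents.** Boundaries, alphas, the 0.0492 threshold and 24 patients: section 6.2. Four follow-up visits and three sites: section 3.1. Two race categories: inclusion criterion 12. SD 2.6 and 20% loss: section 6.1. Allocation 1:1:1:1: section 3.3. The 0.0492 is taken as given; its derivation is not examined here.

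**Step 1: reproduce the stated pairs.** Two-sided normal tail, 2 × (1 − Φ(c)):

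- 3.428 gives 0.00061 (stated 0.0006)
- 2.431 gives 0.01506 (stated 0.0151)
- 1.985 gives 0.04714 (stated 0.0471)

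All three match, so these are normal critical values.

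**Step 2: size of the model.**

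- Covariance parameters, unstructured over four visits: 4 × 5 / 2 = 10.
- Fixed effects with class or cubic time: 4 treatment cells × 4 time terms = 16, plus site 2, gender 1 and race 1, giving 20.
- Fixed effects with linear time: 4 × 2 = 8, plus the same 4, giving 12.
- Between-patient df: N − 8 (intercept, 3 treatment terms, 4 covariate terms). This is 12 at N = 20 and 16 at N = 24.

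**Step 3: tail areas on t.**

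- N = 20: P(|t12| > 3.428) = 0.0050, and 0.0050 / 0.0006 is about 8. The t value that gives 0.0006 is 4.610.
- N = 24: the normal value for 0.0492 is 1.967, and P(|t16| > 1.967) = 0.067. The t value that gives 0.0492 is 2.128.
- 95% interval multiplier at N = 24: 2.120 on 16 df against 1.960 normal, a ratio of 1.08.

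This step needs no assumption beyond the df.

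**Step 4: null simulation at N = 24, threshold 0.0492.** A t reference corrects the distribution but not the standard error, so the stated REML model was simulated with no treatment effect. Assumptions that are not in the documents: within-patient correlation 0.6, monotone loss, and one third each women and African American. The contrasts were the PUFA effect at 12 months and averaged over visits. The ranges below cover two sets of runs, with complete data and with 20% loss. The larger set had 1,600 runs per class-time case and 4,000 per linear-time case, with Monte Carlo standard errors of about 0.55 and 0.35 percentage points.

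| Time in model | Normal reference | t on 16 df | Kenward-Roger |
|---|---|---|---|
| Class (20 fixed effects) | 8.0-9.0% | 5.5-6.4% | 4.9-5.6% |
| Linear (12 fixed effects) | 11.0-12.9% | 8.9-10.5% | 5.6-6.5% |

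Sensitivity to the assumed correlation: for the 20-effect model with visit correlations of 0.5-0.7 and 20% loss (1,796 fits), the three figures were 8.2-9.6%, 6.2-7.1% and 5.7-6.5%. At 60 patients (700 fits) all three references were close to nominal.

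The smaller mean model does worse. With linear time, the estimated unstructured covariance is used to weight the visits, and an uncorrected standard error ignores the uncertainty in those weights.

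Because 0.0492 is almost 0.05, these rates are close to the non-coverage of the 95% intervals. With linear time and t on 16 df, coverage is roughly 90%.

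**The case against.** **The critical values are history.** The first look is past, and the looks at 40 and 60 will not take place. The one live threshold is already a p-value. This stands: no figure for the look at 20 patients changes the remaining analysis.

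**The rule at 20 patients can be read strictly.** It asks for the critical value and its alpha; if both must be met, the stricter p-value governs. This also stands. For the 20-effect model, p < 0.0006 on 12 df occurred in 0-0.2% of simulated trials. At enrolment of the 20th patient few would have 12-month data, so any simulation of that look is approximate. A reader might infer that the trial was stopped, or nearly stopped, for efficacy on a faulty boundary. The documents report neither the result of that look nor the reason for termination, so they do not support this.

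**PROC MIXED reports t statistics, so a normal reference is not the expected output.** This is fair. With a t reference and class time, type I error is about 6% against 4.92%, and Kenward-Roger then changes little. A reader might conclude that the stated alphas definitely fail, or that the large number of fixed effects is the cause. Neither is supported: the reference is unstated, and the 12-effect model is the one with more inflation. But the plan allows BIC to choose that model, and there t df alone leaves about 9-10%.

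**Efficacy is exploratory.** Feasibility and safety are the primary objective in section 2. This limits the consequence but does not remove it: section 3.3 lists efficacy within the primary endpoint, section 6.2 sets a threshold to four decimals, and the intervals are a stated product of the study.

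**Conclusion.** The point holds as a gap in the analysis specification that can affect results. The planned boundaries were normal approximations, and no small-sample correction is set for a model now fitted to 24 patients. The 0.0492 threshold and the 95% intervals are therefore not assured. That is the supported claim, not that they must fail.

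The size depends on two choices the plan leaves open. With a t reference, type I error is about 6% for class time and about 9-10% for linear time. With a normal reference it is about 8% and 12%. Kenward-Roger brings both models to about 5-6%. The tail areas follow from the plan's own numbers and the df count. The simulated rates rest on an assumed correlation of 0.6, 20% monotone loss and the contrasts chosen here.

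**What to change.** In section 6.2, specify DDFM=KR in PROC MIXED for every efficacy contrast, p-value and 95% interval in the 24-patient analysis, including the Brief Pain Inventory, SF-12 and sex-by-treatment models. State that efficacy thresholds are judged on the p-value scale. For the past and cancelled looks, a note that their critical values were normal approximations is enough.

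The cost is one procedure option, two sentences and wider intervals. Standard errors rise by about 3% with class time and about 14% with linear time. In the simulated class-time model with 24 patients, the median half-width at month 12 goes from 2.60 to 2.69 points (0.09 / 2.60, about 3.5%). With linear time, the extra width reflects uncertainty that the uncorrected interval leaves out.
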